Specific Aim 3: Conduct a pilot randomized controlled trial of the brief, Veteran-targeted PCI in a sample of recent Veterans with stress-related mental health disorders (n=48) to assess feasibility and preliminary efficacy.

Hypothesis 3a: The brief PCI will be shown to be feasible as evidenced by successful rates of recruitment, attendance at intervention sessions by Veterans, and interventionist fidelity to the intervention.

Hypothesis 3b: Compared to a health and wellness control intervention, participation in the brief, Veteran targeted PCI will result in significant increases in (1) Veteran PCC behaviors in mental health care encounters and (2) functioning in domains of health, purpose, and community.

Secondary analysis: Comparing the RCT arms, explore (1) Veteran attrition from VA mental health care via chart review and (2) Veteran self-assessment of levels of clinical symptomology with the DASS-21, AUDIT, DAST 10, and PCL-5.

2 * Discuss the research design including but not limited to such issues as: probability of group assignment, potential for subject to be randomized to placebo group, use of control subjects, etc.:

Aim 1: 35 recent Veterans with stress-related mental health disorders and their VA mental health providers will consent to audio-recording of one treatment encounter. (There is no randomization or group assignment.)

Aim 2: Two focus groups of 4-6 Veterans each will be held. We will also conduct a clinical demonstration of the PCI with 10 Veterans to examine acceptability and further refine the intervention. Participants will complete the three session intervention and participate in a qualitative interview about their experience. (There is no randomization or group assignment.)

Aim 3: We will conduct a pilot randomized controlled trial of the PCI (n=48) to assess feasibility and preliminary efficacy. 24 participants will be randomized to a health and wellness control condition and 24 to the experimental treatment condition.

3 * Describe the relevant prior experience and gaps in current knowledge. Describe any relevant preliminary data:

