After all survey and coding data has been captured into the database, frequency tables for all variables and histograms for continuous variables will be examined. Missing data and potential errors will be investigated and resolved. Scales and subscales will be scored. Normal Q-Q plots will be examined for continuous variables to check normality, skew, and to assess whether transformations are needed to examine the associations. Descriptive statistics will be calculated on demographic variables to characterize the sample. To assess PCC behaviors, descriptive statistics will be calculated for all PCC subscales and variables from coding, including: minimum, 25th percentile, median, mean, 75th percentile, maximum, and standard deviation. The descriptive statistics will be collected and displayed in tables separately for Veterans and providers along with histograms to visually assess overall distributions and variability. For these analyses, each patient-prescriber dyad will be treated as a unique encounter. Proportions of patients and providers meeting certain levels of the 4 components of PCC will also be calculated along with 95% confidence intervals.

Aim 2 data analyses

Aim 2 Veteran focus groups and refinement of materials. Once a draft of the PCI is developed, two focus groups of 4-6 Veterans each will be held (1-1.5 hours each). The focus groups will be led by the PI and observed by the coordinator, who will also take observational notes. Participants will be asked to comment on and critique the draft PCI structure and content. Because the goal is to elicit concrete suggestions and feedback with which to develop the PCI, focus group transcripts will not be coded to identify overarching themes or quotes. Rather they will be used to identify suggestions for PCI modification. Study team members will utilize the transcripts, observational notes, and personal observations to summarize focus group discussion and suggestions from focus group participants into an organized document for the EAP. In addition, relevant study team members will present the findings and be available for questions during EAP Meeting 3.

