Appointment recording coding. Similar to the procedures described in 3b11 (Aim 1 data analysis), the PI will work with two research team staff members to code recorded appointments with the MPCC. We will all code the first 4 recordings to confirm coder competence and establish interrater reliability. After the first 4 recordings coders will code recordings individually until every seventh recording. Every seventh recording I and the research team members will again all code the same recording and check for agreement. Through this process 20% of the recorded appointments will be coded and compared by multiple coders.

Aim 3, hypothesis 3a. The brief, Veteran-targeted, PCI will be shown to be feasible as evidenced by adequate rates of recruitment, Veteran attendance at PCI sessions, and interventionist fidelity to the PCI. We will track: (1) actual recruitment compared to recruitment goals; (2) number of sessions each participant attends, enabling us to identify initial engagement, overall attendance rates, and drop-out; (3) number of reminder and outreach contacts required to keep participants engaged, indicating how much staff time is required to successfully facilitate involvement; (4) interventionist adherence to the PCI; and (5) qualitative feedback from a subsample of pilot RCT intervention arm participants as described in section 3d9. Recruitment feasibility will be assessed by a proportion equal to # of patients who sign consent / # of patients approached. To account for sampling variability we will also calculate a 95% confidence interval. Attendance will be collected at each PCI session and stored in our database. We will calculate the proportion of sessions attended for each participant. Feasibility will be demonstrated if at least 80% of PCI participants attend at least 2 out of 3 of PCI sessions. Interventionist fidelity will be measured by our interventionist adherence rating scale. A random selection of 25% of the PCI session recordings will be analyzed, stratified by month over the course of the pilot RCT, to examine potential changes in the way the PCI is delivered over time. After study completion we will calculate overall percentages for each item of the scale to assess overall fidelity. Interventionist fidelity will be demonstrated if at least 90% of interventionist behaviors in the analyzed PCI sessions have been rated acceptable or excellent.

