Aim 3, hypothesis 3b. We hypothesize that compared to control participants, participation in the brief, Veteran-focused, PCI will result in significantly greater increase in (1) Veteran PCC behaviors in mental health care encounters as measured by the MPCC and (2) functioning in domains of health, purpose, and community as measured by the VR-36 and WHODASS. Our overall approach will be to compare group means using a mixed model, accounting for common providers among participants with a random provider effect. If

an out of balance prognostic covariate is found in baseline comparisons this variable will also be included in the model, although the number of covariates that can be adjusted for will be limited by the sample size. We chose to use mixed models versus GEE (generalized estimating equations) to avoid bias due to unequal cluster sizes or sample size.

More specifically, for hypothesis 3b(1) to compare the treatment arms on PCC behaviors in mental health care encounters we will use the MPCC, assessed only at time point 2. The independent variable will be the treatment group indicator. For hypothesis 3b(2) to examine whether relative to control the treatment group has greater functioning (subscales of the VR-36 and WHODAS), we will compare group means at time points 3 and 4 using a linear mixed model ANCOVA. The comparison at time point 3 will be primary and at time point 4,

secondary. For this hypothesis, after adjustment for baseline, there will be 2 repeated measures (time points 3 and 4) which will be assumed to be correlated (i.e. thru correlated error terms). However, contrasts will be specified in order to compare the groups at time point 3, separately from time point 4.

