In addition we will conduct exploratory analyses using data collected from the RCT examining whether Veteran perception of satisfaction with VA mental health care, therapeutic alliance, and personal agency differ between control and treatment conditions.

Mediation Analyses. As an example, the mediating effect of Personal Agency (from PAM) between the PCI intervention (PCI vs Control) and VR-36 Social Functioning subscale will be based on Sobel's test for an indirect effect. The first step is to test whether there is a total effect (path c'), i.e. a treatment group difference on the Social Functioning subscale at TP3. If there is a significant group difference on Social Functioning, then the second step will be to estimate both the effect of the PCI on Personal Agency (mediation path 'a') and the direct effect of Personal Agency on Social Functioning (mediation path b) when the treatment indicator is also in the model. Sobel's test tests the significance of the product $a \cdot b$ (indirect effect) by using a bootstrap 95% 'bias corrected' confidence interval. Same procedure will be used for other outcomes and mediators.

Moderator Analyses. Moderators will be tested by simply adding the main effect term and interaction term between the moderator and treatment group indicator to the main outcomes analysis model. Moderators must be assessed pre-intervention, hence at baseline. Evidence of moderation is provided if the interaction term is statistically significant. Moderators can be examined for MPCC (TP2), and the health and functioning outcomes (TP3).

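### Does hypothesis 3b need a named primary score and error control before its efficacy results can be read?

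*Combined protocol and SAP*

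**What the plan says.** The aims (Justification, Objective, & Research Design, item 1) predict that the "PCI will result in significant increases in (1) Veteran PCC behaviors in mental health care encounters" and, as a second part joined by 'and', in functioning in the domains of health, purpose and community. The analysis plan (Sample Size and Data Analysis, item 2, hypothesis 3b) repeats the prediction in similar terms.

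For the first part, "we will use the MPCC, assessed only at time point 2". For the second, the aim is to show "greater functioning (subscales of the VR-36 and WHODAS), we will compare group means at time points 3 and 4" by a baseline-adjusted linear mixed model. The only ranking is by time: "The comparison at time point 3 will be primary" and the later one secondary. No subscale is listed, no MPCC score is singled out, and neither a significance level nor a success rule is given.

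Under Mediation Analyses, with VR-36 Social Functioning as the example: "If there is a significant group difference on Social Functioning, then the second step will be to estimate" the mediation paths. Then: "Same procedure will be used for other outcomes and mediators".

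Item 1 of the same section makes feasibility the primary goal, disclaims adequate power for small effects, and gives power of .80 for d = .65 with 19 per arm at TP3. Hypothesis 3a has numerical criteria for attendance (80%) and fidelity (90%).

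**The concern.** A hypothesis worded in terms of significance normally comes with a score, a level and a rule. Here the set of functioning scores is open. The MPCC could also yield several scores: in Aim 1, "descriptive statistics will be calculated for all PCC subscales and variables from coding", and the Aim 3 recordings are coded in a related way ("Similar to the procedures described in 3b11 (Aim 1 data analysis), the PI will work with two research team staff members to code"). The neighbouring hypothesis 3a has thresholds, so the silence on 3b stands out.

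If any single significant subscale could be presented as support, a chance result might be reported as confirming 3b, lead on to a mediation analysis, and influence the larger trial that the investigator intends to propose. Feasibility conclusions would not be touched.

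**Working it through.** **Inputs from the document.** 24 randomized per arm; 19 per arm with TP3 data; d = .65; correlation of baseline with follow-up r = .7; MPCC measured once, without baseline.

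**Assumptions.** Two-sided .05; 3 scores (one per domain) or 8 scores; equal correlations of .5 to .7 between scores; MPCC independent of the functioning scores; provider effect ignored.

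**1. The plan's power.** Residual SD factor = √(1 − .7²) = √.51 = .714. Noncentrality = (.65/.714) × √(19/2) = 2.805. Normal approximation: Φ(2.805 − 1.960) = .801, which reproduces the stated .80. With the t distribution on 35 df it is .779. So the figure describes one baseline-adjusted score tested at two-sided .05. The plan does not claim it for the MPCC, where the same d without a baseline gives .597 with 24 per arm and .496 with 19.

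**2. False support with no true effect, by reading of 3b.** The first row is simulated; the others follow from it.

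| Reading | 3 scores, correlation .7 / .5 | 8 scores, correlation .7 / .5 |
|---|---|---|
| Any one functioning score, either direction | 11.0% / 12.5% | 19.0% / 25.0% |
| Any one, predicted direction only (half) | 5.5% / 6.3% | 9.5% / 12.5% |
| MPCC and any one functioning score (× .05) | 0.6% / 0.6% | 1.0% / 1.3% |

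The second row matters because 3b predicts increases, so a significant result favouring control is not support. In the third row, for example, .05 × .125 = .006 and .05 × .250 = .0125. If every score had to pass, unadjusted tests would not inflate error at all.

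At a correlation of .3, the first row becomes about 14% and 30%.

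**3. What adjustment would cost.** With Holm across four scores (three functioning and one MPCC), the hardest case tests at .05/4 = .0125. Power for d = .65 on a functioning score then falls from .779 to .572, and the detectable effect rises from d = .67 to .81. With all four effects real, power is .65 to .66.

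**4. The mediation step.** A significance gate reduces the number of mediation tests compared with running them all. An outcome with no effect passes it about 5% of the time, and the indirect effect must then clear its own bootstrap 95% interval. The paragraph also comes after the one headed secondary and exploratory analyses.

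**5. The MPCC.** The Aim 1 sentence describes summary tables for Veterans and providers. The Aim 3 cross-reference concerns how recordings are coded and checked between coders. Neither announces several between-arm MPCC tests, and 3b is confined to Veteran behaviors.

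**The case for a change.** The strongest case for a change is that the pilot label does not tell a reader which score decides 3b. The plan labels its symptom subgroup analyses exploratory because of the small sample, but gives 3b neither that label nor a threshold. Naming scores would need only a dated amendment with no added visits. It would be most useful before results by arm are seen, since participants were already enrolled and an unblinded team member, possibly the principal investigator, may deliver control sessions.

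Much of this stands. The supplied text does leave the scores and the rule unwritten. The low figures for the two-part reading also assume no effect anywhere: if the MPCC truly improves, that half of the requirement gives little protection, and the functioning part returns towards the any-one rates.

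What does not stand is the step from an unwritten rule to a material risk. The high figures need the reading that the wording favours least, counts that the document does not supply, and results in the wrong direction counted as support. Adding a formal procedure is not clearly better either: it costs up to .21 in power per functioning score (.78 − .57) in a trial already limited to medium-to-large effects. Reporting estimates alone is equally defensible. The text also cites sections of a fuller plan (3b11, 3d9) that are not in the document, so the scores may be named there.

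**Conclusion.** The observation is accurate but calls for no change. It combines a missing detail with a fair trade-off. The primary time point is fixed, the model is specified, the three domains are named, and an analyst can choose one suitable score per domain and treat 3b as the preliminary evidence the aim calls it. Whether to adjust, or to rely on estimates with confidence intervals, is a matter of judgement in a pilot of 24 per arm.

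Under no effect, false support is about 1% or less on the two-part reading with three to eight scores. It is 5.5–6.3% (three scores) or 9.5–12.5% (eight) if any one favourable functioning score sufficed. These figures rest on two-sided .05, correlations of .5 to .7, assumed score counts, an independent MPCC and no provider effect. Readers of the results should not treat a single significant subscale as settling 3b. The feasibility conclusions, on which the pilot is mainly judged, are unaffected.

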Veterans' actual involvement in care. Second, while self-evaluation provides valuable information about Veteran preferences for and perceptions of mental health care interactions, the use of the RIAS also allowed comparison of survey responses to behaviors in actual appointments. Analyses of the recordings found that African American Veterans had shorter appointments (18.6 minutes, SD=10.8) compared to White participants (22.4 minutes, SD=11.9; p=.034). Notably, this difference seemed to be solely linked to differences

in patient behaviors, not prescriber behaviors. There were no differences associated with race in the amount or type of prescriber statements. However, African American Veterans spoke less than White Veterans, (average 25 fewer statements per 15 minute interval). Specifically they had significantly lower rates of psychosocial information giving, emotional rapport, and procedural statements, and were less likely to express disagreement or criticism to their prescriber. The difference was greatest in psychosocial information giving, where African American Veterans made 10 fewer statements per 15 minutes about lifestyles or psychosocial environment.

4 * Provide the scientific or scholarly background, rationale, and significance of the research and how it will add to existing knowledge:

Recent Veterans are at significant risk of experiencing stress-related mental health disorders such as PTSD, depression, anxiety, and substance use disorders, and subsequently, difficulties in health, home, purpose, and community functioning. Research indicates that recent Veterans in VA treatment for stress-related mental health disorders have unacceptably high dropout rates and that such

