We're following up about your participation in a VA research study. It's time to schedule our final meeting so we can update you on our progress. Please use the following link to show when you are available for this meeting. If you have any trouble with the scheduling link or would like speak with a study team member you can email us at [contact] or contact us at XXX-XXX-XXXX.

We cannot guarantee email is secure so please do not reply back to this message with any personal information or personal health information.

Thank you and have a great day!

3. Email script 2 for EAP scheduling

Subject: research study follow up

Hello,

We're following up about your participation in a VA research study. Based on everyone's availability, we are hoping to schedule the meeting for DATE at TIME. The meeting will take place at LOCATION (phone/telehealth/in person). Please reply YES or NO to this email to confirm this works for you. If you had any trouble with the scheduling link or would like speak with a study team member you can email us at [contact] or contact us at XXX-XXX-XXXX. We cannot guarantee email is secure so please do not reply back to this message with any personal information or personal health information.

Thank you and have a great day!

Aim 3 quantitative data will be collected at baseline, post-RCT participation, and 3 month and 6 month follow-up and qualitative data will be collected at 3 month or 6 month follow-up. Feasibility will be assessed with study administration data on engagement and participation in the intervention and preliminary efficacy will be evaluated via coded Veteran/provider encounters and quantitative analysis of functioning from self-report surveys. Further needed intervention modifications will be identified from qualitative interviews.

Participants will have the option of completing the surveys in person, by phone, or by mail. If participants completing the surveys by mail have not returned the surveys within one week a study team member will follow-up by phone. Participants completing the surveys by phone or mail will be mailed their participation compensation upon receipt of the survey data.

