Aim 3, secondary and exploratory analyses. Secondary preliminary efficacy outcomes in the treatment group are (1) Veteran attrition from VA mental health care as compared to the control participants as established via chart review at TP3 and TP4 and (2) levels of Veteran self-assessment of clinical symptomology with the DASS-21, AUDIT, DAST 10, and PCL-5 at time points 1, 3, and 4. For (1) we will determine the proportion of scheduled mental health care appointments that participants did not attend or canceled between TP1 and TP3 and TP3 and TP4, via chart review for the treatment and control groups. Proportions rather than raw counts will be analyzed to account for different patients having different numbers of scheduled appointments. If the number of different values for the proportions is few (say less than five), we will either define ordinal categories or dichotomize the proportions as there may be a lot zeros. We would then use a logit mixed model ANCOVA. If there are more than five unique values, but the distribution has substantial skew, we will again use an ordinal logit mixed model. Otherwise, if the distribution is close to symmetric we will use a linear mixed model ANCOVA. In either case we will use semi-parametric 'sandwich' standard errors known for their robustness to deviation from model assumptions. For (2), the self-assessment symptom measures will be analyzed to assess clinically significant change. Due to the heterogeneity of the inclusion diagnoses this may involve forming subgroups based on baseline symptom severity, and therefore these analyses will be exploratory due to the small sample size. Additionally, we will form z-scores for each symptom measure and pool scores across symptom type as it is expected that all participants will have significant severity on at least one symptom measure. The DASS-21 and DAST 10 scores map onto five clinically meaningful levels and the AUDIT score maps onto four clinically meaningful levels. A mixed effects ordered logit model will be used to account for the ordinal levels of the response variable and will include random provider effect. A 10 point change on the PCL-5 has been established as clinically significant, hence, binary indicator variables will be constructed to indicate 10-point improvement (or not) at both TP3 and TP4. A mixed effects logistic regression model with random provider effect will be used to compare probability of 10-point improvement between the two groups.

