- If meeting face-to-face with a veteran for their individual session(s) is not possible then a trained study interventionist may (1) transport a study audio recorder to capture the audio of any individual session(s) completed via telehealth visit or (2) utilize the VA's protocol for Recording in CAG using Audacity Application and will export the recording to a restricted access VA sharedrive. If the interventionist uses an audio recorder they will utilize their locked HIPAA bag to transport the recorder, to ensure its protection.

- If meeting face-to-face with a veteran for their regularly scheduled mental health care is not possible and the veteran has provided consent to record one of their regularly scheduled mental health care appointments, then the study team will approach the veteran's mental health care provider to ask if they are willing to utilize the VA's protocol for Recording in CAG using Audacity Application. If they agree then the study team will make arrangements with the clinician to receive the recording via a sharedrive and immediately export the recording to a restricted access VA sharedrive.

Behavioral Intervention

You indicated that this study involves psychosocial or behavioral interventions.

1 * Describe the intervention (duration, number of sessions, focus, etc.):

Aim 3

Treatment condition. We anticipate that the person-centered intervention (PCI) will be comprised of three, one-hour sessions offered over three to six weeks, scheduled at the participants' preference. Sessions will be one-on-one with the interventionist. The PCI sessions will be offered in a private room in the same buildings that VA mental health services are located in, on the two respective VAMHCS campuses OR will be offered via VA Video Connect, the VA's telehealth program which uses encryption to ensure a secure and private session, OR phone.

Control condition. The control condition will be an educational health and wellness intervention for stress related disorders that will match the experimental condition for time and attention. The control condition will be three, one hour, individual sessions covering the symptom cycle, managing stress, and identifying social supports. The interventionist will be a non-blinded member of the research team such as the

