PI or coordinator. The control sessions will be offered in a private room in the same buildings that VA mental health services are located in, on the two respective VAMHCS campuses OR will be offered via VA Video Connect, the VA's telehealth program which uses encryption to ensure a secure and private session, OR phone.

ID: VIEW4E0BC12A9F800
Name: v2_Behavioral Interventions

Data Collection/Record Review

You indicated on the "Type of Research" page that your study involves data collection or record review (i.e., chart review, not self-report).

1 * What type of data will be collected/analyzed in this study? (Check all that apply)

Retrospective/Secondary Analysis (data has already been collected at the time of initial IRB submission)
 Prospective (data is not yet in existence and/or collected)

2 * Will this study involve adding data to a registry or database for future use?

Yes No

3 * Will the data be released to anyone not listed as an investigator on the protocol?

Yes No

3.1 If Yes, give name(s) & affiliation(s):

ID: VIEW4E0E25A8CA400
Name: v2_Data Collection / Record Review

Prospective Data

You indicated that the study involves the collection of prospective data.

1 * Where is the data being collected from? (Check all that apply)

- Medical records
- Medical images
- Commercial (for profit) entity
- Publicly available records
- Schools
- Other

1.1 If Other, please specify:

2 * What data fields will you have access to/collect for the study? For example, name, initials, date of birth, Social Security number, income, demographic information, family units, housing, etc.

The following information will be collected from VA medical records: 1) Veteran name 2) Veteran address 3) period of military service 4) mental health/substance use diagnoses 5) initial date of mental health and/or alcohol/drug abuse treatment service use 6) last date of mental health and/or alcohol/drug abuse treatment service use.

Near the end of study participation, Veteran service use data will be collected for the period of time the Veteran was enrolled in the study. This will include number of mental health, physical health, and Whole Health appointments and appointment dates.

You can also upload a copy of the data fields/variables to be collected for the study:

Name	Created	Modified Date
------	---------	---------------

There are no items to display

ID: VIEW4E0E25B643800
Name: v2_Prospective Data

Clinical Trial Registration

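### The secondary outcome called attrition from VA mental health care is scored as the share of scheduled appointments missed or cancelled, which measures attendance among Veterans with appointments and loses leavers who have none

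*Combined protocol and SAP*

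**What the plan says.** Under Justification, Objective, & Research Design (item 1, Aim 3 secondary analysis), the plan will "explore (1) Veteran attrition from VA mental health care via chart review". Under Sample Size and Data Analysis (item 2, Aim 3 secondary and exploratory analyses), the outcome is "Veteran attrition from VA mental health care as compared to the control participants as established via chart review at TP3 and TP4". The only scoring rule follows there: "the proportion of scheduled mental health care appointments that participants did not attend or canceled between TP1 and TP3 and TP3 and TP4". Proportions are preferred to counts because Veterans differ in how many visits they have scheduled. The model (logit, ordinal logit or linear mixed) is chosen from the number of distinct values and the skew.

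Nothing defines leaving care, and nothing covers a window with no scheduled visit. The remark about many zeros concerns proportions equal to zero, that is, Veterans who missed nothing.

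Three other places matter:

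- **Rationale** (same Justification page, item 4): "recent Veterans in VA treatment for stress-related mental health disorders have unacceptably high dropout rates".
- **Timing** (Study Procedures, item 1): "Aim 3 quantitative data will be collected at baseline, post-RCT participation, and 3 month and 6 month follow-up". I read these as TP1 to TP4 in order. The second recruitment email places the later two about three and six months after the sessions end. The sessions themselves are "three, one-hour sessions offered over three to six weeks" (Behavioral Intervention, item 1).
- **Chart data** (Prospective Data, item 2): "Veteran service use data will be collected for the period of time the Veteran was enrolled in the study", and "This will include number of mental health, physical health, and Whole Health appointments and appointment dates". The same item lists the last date of mental health or substance use service. No analysis section uses that date or the appointment dates to score attrition.

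**The concern.** The outcome's name and the rationale are about leaving care. The score is about keeping appointments. The two differ in two ways.

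1. A Veteran with nothing scheduled in a window has no score and by default is missing for that window. This would arise mainly in TP3-TP4. Leaving care is one cause, so missingness can depend on the event being measured. Planned completion and widely spaced visits give the same 0/0.
2. Among Veterans with a score, leaving and staying can look alike. One who attends 4 of 5 visits and then leaves with nothing further booked scores 1/5 = 20%. One who stays and misses 2 of 10 also scores 20%.

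This is the only listed outcome for leaving VA mental health care, and the VA-Specific Criteria section says a larger trial will be informed by the findings. A difference in attrition could be missed, or passed on too small.

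**Working it through.** **Plan's own figure.** The plan gives no power or expected rate for attrition. Its one design figure, power .80 for d = .65 with 19 per arm and r = 0.7, reproduces at .801 (normal approximation, two-sided 5% assumed). It concerns the ANCOVA outcomes and does not bear on this point.

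**Inputs.** From the plan: 24 randomised per arm. Assumed: stayers miss 25% of visits; 36% v 18% have left before the window opens (true difference 0.18), with 20% v 10% as an alternative. The 36% borrows the average PTSD-treatment dropout quoted under Supporting Literature; it is not a rate of leaving VA mental health care. A share b of leavers still have booked visits and miss them all; the rest have nothing scheduled.

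**Expected score in TP3-TP4.** With q the proportion who left, and missing visits unrelated to leaving:

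mean score = [(1 - q) × 0.25 + q × b] / [1 - q(1 - b)]

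- b = 1: 0.520 v 0.385, difference 0.135.
- b = 0.5: 0.340/0.820 = 0.415 v 0.295/0.910 = 0.324, difference 0.09.
- b = 0: 0.25 v 0.25, difference 0.

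The number scoring 0/0 is 24 × (0.36 + 0.18) × (1 - b).

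**Allowing leavers to be those who miss more.** Simulation with individual miss rates from Beta(2,6), correlation 0.5 with leaving, and 20,000 trials per cell:

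| Leavers with booked visits | Score difference, 36% v 18% (true 0.18) | 0/0 of 48 (36% v 18%) | Score difference, 20% v 10% (true 0.10) |
|---|---|---|---|
| 0% | -0.02 | 13 | -0.01 |
| 10% | +0.01 | 12 | 0.00 |
| 25% | +0.04 | 10 | +0.01 |
| 50% | +0.08 | 6.5 | +0.04 |
| 100% | +0.13 | 0 | +0.07 |

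**TP1-TP3.** Taking 18 weeks (about 13 plus three to six of sessions), about 8 scheduled visits and a uniform leaving time, the 36% v 18% difference is 0.00, +0.03 and +0.06 at 0%, 50% and 100% booked.

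**The yes/no alternative on the same assumptions** (no attended visit in the window; visits every 2, 4 or 6 weeks; leaving uniform over the 18 weeks; TP2 at week 5):

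- TP3-TP4: recovers 0.16 to 0.18 of 0.18.
- TP2-TP3: recovers 0.07 to 0.085 of 0.18 and flags about 40% to 60% of leavers, because many attend at least once in the window before going.

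**Errors of the alternative.** Of those who leave inside a 13-week window, 64% to 87% are counted as retained. A stayer is wrongly counted as having left if every scheduled visit is missed: 0.25 with one visit, (2 × 3)/(8 × 9) = 0.083 with two, 0.004 with six.

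**Precision.** 9/24 v 4/24 is 37.5% - 16.7% = 21 points, Newcombe 95% CI -4 to 43. Power is .30 for 36% v 18% and .17 for 20% v 10% if everyone is classified correctly.

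**The case against.** **Weight.** The aims say this outcome will be explored. Feasibility is the primary goal, n = 48 was set by resources, and the feasibility thresholds concern PCI session attendance and fidelity. No decision rests on the attrition score. This stands and keeps the priority low.

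**Definition.** Missed-visit share is a legitimate engagement measure, and the plan's own background uses other notions of dropout, such as not completing a recommended course. This stands in part. No visit in a window is one reasonable definition, not the only one. Whichever is chosen, the label and the missing denominator rule still need attention.

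**The alternative is also imperfect.** This stands. In TP2-TP3 the yes/no rule loses more than half of the difference, against +0.03 to +0.06 for the planned score in TP1-TP3 when half or all leavers have booked visits. Its clear advantage is in TP3-TP4, for those who had left by TP3. The power figures above are optimistic: with misclassification, TP2-TP3 power is about .12 for 36% v 18% and .05 to .08 for 20% v 10%.

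**A stronger reading to avoid.** A reader might infer that the score would point the wrong way, or that every 0/0 Veteran has dropped out. The documents support neither. A reversal appears only when almost no leaver has a booked visit, and it is then about 0.01 to 0.02. An empty window may reflect completed treatment or sparse scheduling.

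**Conclusion.** The concern holds as a mismatch between the outcome's name and its scoring rule. Followed exactly, the rule measures appointment attendance among Veterans with something scheduled, drops leavers with nothing booked, and cannot always tell a leaver from a stayer. Leavers with booked visits are partly captured.

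The mismatch and the missing 0/0 rule rest on the text alone. The size of the consequence is unknown: the documents give neither the rate of leaving VA mental health care nor the share of leavers with visits still booked. Under the assumed inputs, the TP3-TP4 difference lies between -0.02 and +0.13 against a true 0.18, and between -0.01 and +0.07 against a true 0.10. It was smaller than the attrition difference in every case tried.

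No primary comparison and no feasibility criterion is affected. This is a low-priority improvement to an exploratory outcome, worth making before analysis so that the handling of empty windows is not settled after the data are seen.

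**What to change.** 1. **Rename the planned score and show its gaps.** Call it appointment attendance among those with at least one scheduled visit in the window, and report by arm the number with none.
2. **Add a yes/no attrition estimate for every randomised participant.** The main version is no attended VA mental health visit in TP3-TP4. Anchor the window at three and six months after sessions end, and state an anchor for those who attend no session. Chart dates let participants who miss the TP3 or TP4 assessment be scored. Extract attended, missed or cancelled status at the same review, since the planned score already needs it. Use the last service date too if it is collected at follow-up; the plan does not say whether it is. If TP2-TP3 is reported, label it as insensitive.
3. **Handle the ambiguous cases openly.** Report documented planned completion as its own category, with a sensitivity analysis counting it either way. Give all-left and none-left bounds for formal withdrawals, because the Withdrawal of Participants section allows no new data after withdrawal.
4. **Present the risk difference with a 95% CI as an estimate, not a test.**

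**Cost.** SAP wording and slightly more chart extraction. Precision will be low, most Veterans who leave after TP3 will not be captured, and some stayers with few visits will be counted as having left.
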